The objective is to conduct a pilot comparative effectiveness trial with MODEL Clinical Research (MODEL), Research Division of Bay West Endocrinology Associates (BAY), an affiliate of GBMC and a member of the Johns Hopkins Clinical Research Network, to compare two treatment strategies (regimen using traditional drugs only vs. regimen including incretin-based classes of medication) in the elderly patients with type 2 diabetes on time to achieving glycemic target, overall hypoglycemia, weight gain, adverse events, and quality of life. This study will provide preliminary data on a 'preferred' anti-diabetic regimen for elders by comparing and quantify short-term effects from treatment regimens in diabetic elders.

3. Background (briefly describe pre-clinical and clinical data, current experience with procedures, drug or device, and any other relevant information to justify the research)

Date: June 11, 2013

Principal Investigator: [name]

Application Number: NA_00052707

The optimal approach to glucose control for patients with type 2 diabetes is uncertain, particularly in older patients. For over a decade, glucose lowering recommendations have been primarily based on the results of the United Kingdom Prospective Diabetes Study (UKPDS) in middle-aged patients with new onset diabetes⁴. This trial showed that patients with an average HbA1c of 7.0% had a lower rate of microvascular complications than patients with HbA1c of 7.9%. More recently completed trials suggest possible harm associated with tighter targets (e.g. HbA1c 6.5%)^{5, 6}. Nonetheless, geriatric diabetes care guidelines also have endorsed pursuing an A1c<7.0% for healthy older patients with life expectancies greater than 5 years⁷, admittedly without a firm evidence base. However, even traditional targets for glycemic control may include treatments that increase the chances of polypharmacy, hypoglycemia, weight gain, geriatric syndromes, and worsened quality of life. Severe hypoglycemic episodes have been associated with the development of dementia⁸; polypharmacy has also been shown to increase risk of injurious falls^{9,10}. To develop optimal treatment strategies for diabetic elders, clinical trials specifically conducted in older patients with diabetes are needed.

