Secondary Outcomes: a) Percent achieving glycemic target at 6 month; b) Overall hypoglycemia measured by glucose meter; c) Total cholesterol, HDL cholesterol, and triglyceride; d) Fasting glucose insulin, and fructosamine; e) blood pressure (BP) and heart rate determined by the OMRON 907-XL; f) Weight, height, and waist circumference; g) EQ-5D Questionnaire; h) Diabetes Quality of Life Questionnaire¹⁴; i) Diabetes distress¹⁵ (2 screener questions); j) self-care; k) incontinence¹⁶ (1 question).

Other Data: a) Demographics: tobacco use, health insurance status, education level, and live alone status; b) Medication history including monitoring adherence, which will be self-reported for each of the prescribed medications for glycemic control.

Adverse Events: Hypoglycemic episodes requiring assistance by medical/paramedical personnel, overnight hospitalization, diabetes-related deaths, and other outcomes that the Medical Monitor deems important.

- Statistical plan including sample size justification and interim data analysis.

Date: June 11, 2013

Principal Investigator: [name]

Application Number: NA_00052707

One of the purposes of this pilot trial is to collect needed parameters for future planning of a larger scale confirmatory RCT. To this end, the frequency distribution of parameters of interested will be collected and described at baseline and over follow-up. Repeated measures over follow-up will provide estimate for intra-individual correlations that will be needed in sample size/power determination for the future trial. Repeated measures of HbA1c will also allow examination of HbA1c trajectory over time to inform the feasibility of interpolate the time to reaching HbA1c target threshold based on fixed interval assessments.

Using width of 95% CI as a measure of precision in parameter estimation, a sample size of 30 will provide estimation precision of $\pm 0.31 \times \text{SD}$ for a continuous variable, $\pm 15.5\%$ for a binary proportion of 50%, and $\pm 9.3\%$ for a binary proportion of 10%. For subgroup estimation with $N = 15$ per group, the above precision will be inflated by 1.4.

d. Early stopping rules.

Formal stopping rules are not planned for this pilot trial.

8. Risks

a. Medical risks, listing all procedures, their major and minor risks and expected frequency.

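### The per-arm precision implied for 15 patients is not 95% precision: it is 14% to 22% too narrow, mostly because of the base figures, and the between-arm difference has no precision figure

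*Combined protocol and SAP*

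**What the plan says.** Section 7 (Study Statistics, statistical plan) bases the sample size on estimation precision. The basis is given as "Using width of 95% CI as a measure of precision in parameter estimation". It continues that "a sample size of 30 will provide estimation precision of" plus or minus 0.31 SD for a continuous variable, 15.5% for a proportion of 50% and 9.3% for a proportion of 10%. For estimation in a group of 15 it adds only that "the above precision will be inflated by 1.4". It does not say whether normal or t quantiles were used.

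Section 4c randomizes the 30 participants 1:1, so 15 is the size of one arm. Section 2 (Objectives) gives the aim as "to compare two treatment strategies". Section 7 gives no precision, power or detectable effect for the difference between the strategies. It names planning of a larger confirmatory trial as one purpose of the pilot.

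**The concern.** A reader who applies the factor gets per-arm figures that carry the 95% label. If they are too narrow, the pilot looks more informative about each arm than it can be, and anyone who uses these figures to plan the later trial starts from understated uncertainty. The inflated figure at 10% also gives an interval that runs below zero. That matters for uncommon events such as assisted hypoglycemia, where the upper limit is what one wants to know.

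The comparison is the stated objective, but the paragraph covers only all 30 patients pooled and one arm alone. The difference between two arms is less precise than either, and the reader is not told by how much.

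**Working it through.** **Inputs (Section 7 and Section 4c).** Level 95%, two-sided; N = 30 in total and 15 per arm; half-widths 0.31 SD, 15.5 and 9.3 points; factor 1.4. The choice between normal and t is not stated, so both are shown.

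**Formulas.** Continuous variable: c × SD/√n. Proportion: c × √(p(1−p)/n). Here c is 1.960 (normal) or the t quantile on n−1 df: 2.045 for n = 30 and 2.145 for n = 15.

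**Step 1: the plan's per-arm figures.** 0.31 × 1.4 = 0.434 SD; 15.5 × 1.4 = 21.7 points; 9.3 × 1.4 = 13.0 points.

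**Step 2: 95% half-widths computed directly.**

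| | Plan | Normal | t |
|---|---|---|---|
| N = 30, continuous (SD) | 0.31 | 0.358 | 0.373 |
| N = 30, 50% (points) | 15.5 | 17.9 | 18.7 |
| N = 30, 10% (points) | 9.3 | 10.7 | 11.2 |
| N = 15, continuous (SD) | 0.434 | 0.506 | 0.554 |
| N = 15, 50% (points) | 21.7 | 25.3 | 27.7 |
| N = 15, 10% (points) | 13.0 | 15.2 | 16.6 |

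Per arm, 0.434/0.506 = 0.86 and 0.434/0.554 = 0.78, so the plan's width is 14% (normal) to 22% (t) too narrow.

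**Step 3: where the shortfall arises.**

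- Base figures: 0.358/0.31 = 1.15 (normal) or 0.373/0.31 = 1.20 (t).
- Factor: halving N multiplies a normal half-width by √(30/15) = 1.414, which rounds to 1.4. With t quantiles the multiplier is 1.483 at 95% (1.466 at 90%), which is 5% to 6% above 1.4.
- Together: 1.15 × 1.01 gives about 1.17 (normal), and 1.20 × 1.06 gives about 1.28 (t). The base figures carry most of it.

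**Step 4: possible origin of the base figures.** All three reproduce exactly as a 90% t interval at N = 30 (1.699/√30 = 0.310) and equally as a 95% normal interval at N = 40 (1.960/√40 = 0.310). Other combinations also fit, such as a 90% normal interval at N = 28. None is a 95% interval at N = 30.

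**Step 5: the 10% proportion.** 10 ± 13.0 runs from −3.0% to 23.0%. The directly computed half-widths of 15.2 and 16.6 also cross zero, and so does the 95% normal value for N = 30 (10.7) with no inflation at all. A Wilson 95% interval at p = 10%, n = 15 has centre (0.10 + 0.128)/1.256 = 0.182 and half-width 1.960 × √(0.0060 + 0.0043)/1.256 = 0.158, so it runs from about 2.3% to 34.0%. Since 10% of 15 is not a whole number of patients, the exact intervals for the neighbouring counts are a useful check: 1/15 gives 0.2% to 31.9%, and 2/15 gives 1.7% to 40.5%.

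**Step 6: the between-arm difference, 15 v 15, at 95%.**

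- Continuous: c × √(2/15) SD = 1.960 × 0.365 = 0.716 SD (normal), or 2.048 × 0.365 = 0.748 SD (t, 28 df).
- Both arms at 50%: 1.960 × √(2 × 0.25/15) = 35.8 points (normal); 37.4 with the t quantile.

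Against the ±0.434 SD implied for one arm, the difference is 0.716/0.434 = 1.65 to 0.748/0.434 = 1.72 times as wide.

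**The case against.** **The factor is right.** Under a normal approximation √2 rounds to 1.4. This stands. It is tempting to infer that 1.4 contradicts the plan's own t-based method, because the base figures fit a t interval on 29 df. The documents do not support that: they name no t method, the fit needs a 90% level where the plan says 95%, and a 95% normal interval at N = 40 fits just as well. Even if t was used, the discrepancy is only 5% to 6%.

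**The factor does not cause the below-zero interval.** This also stands. The symmetric approximation causes it, and correct symmetric half-widths cross zero by more. The plan never prints the 10% ± 13 interval, nor does it commit the analysis to symmetric intervals. Giving a Wilson interval is a better way to state the planning figure, not the correction of a slip.

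**It is a pilot with no power claim.** True: the figures are offered for parameter and subgroup estimation, and a reader should not infer that the plan presents ±0.31 to ±0.43 SD as the resolution of the comparison. But parameter collection is only one of the purposes, and comparison is the objective in Section 2. The missing figure is a fair omission to raise, though not an arithmetic error.

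**Calling only the t values correct would be a preference.** Agreed. A t quantile is standard for a mean and not for a proportion, hence the range above. The per-arm figures are too narrow at either end of it.

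**Conclusion.** The concern holds in this form. The per-arm figures that follow from Section 7 are not 95% half-widths for 15 patients under either method. They are 14% (normal) to 22% (t) too narrow: ±0.43 SD against ±0.51 to ±0.55 SD, and ±21.7 points against ±25 to ±28 points at 50%. Most of the error sits in the N = 30 figures and little or none in the 1.4. Whether those figures came from a 90% level or from a sample size of 40 cannot be told from the documents.

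Separately, the precision of the between-arm difference is absent. It is about ±0.72 to ±0.75 SD, or ±36 to ±37 points with both arms near 50%.

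This assumes two-sided intervals, complete data on 15 patients per arm, and a common SD. The figures apply to continuous and binary outcomes; they do not describe precision for the primary outcome, time to target. The importance is moderate: the stated sample size justification is wrong as written, but the conduct of the trial does not depend on it.

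**What to change.** Replace the inflation sentence and correct the base figures with it, naming the method for each:

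- **All 30:** ±0.37 SD (t, 29 df); ±17.9 points at 50% (normal); at 10%, a Wilson interval of about 3.5% to 25.6%.
- **One arm of 15:** ±0.55 SD (t, 14 df); about ±25 points at 50% (normal); at 10%, a Wilson interval of about 2% to 34%, because the symmetric one runs below zero.
- **Between-arm difference, 15 v 15:** about ±0.75 SD (t, 28 df); about ±36 points if both arms are near 50% (normal).

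The cost is the rewriting of one paragraph. The downside is that the stated precision becomes less favourable. No extra patients are needed.
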